To circumvent these limitations, the *Comfort Marker 2.0®* emerged, developed by CIVCO® *Medical Precision*. The device was designed to tattoo set-up markings with controlled and adjustable depth applications. As potential benefits, this feature may translate into less pain for the patient compared to the traditional system, with the benefit of potentiating earlier fading of the ink, with cosmetic advantages.

The present study aims to compare the two systems of cutaneous reference point tattooing: the lancet-based system (hereinafter referred to as the traditional system) and the *Comfort Marker 2.0®* system.

Identification of the research study

Full title: Tattooing of skin set-up markings in Radiotherapy: comparison between the traditional system and the Comfort Marker 2.0®

Short Title: comfoRTattoo

Primary Investigator: [name]

Portuguese Institute of Oncology of Porto FG, [name]
Porto

e-mail: [contact]

Co-Investigator: Tech. [name]

Portuguese Institute of Oncology of Porto FG, [name]
Porto

e-mail: [contact]

Number of investigation sites: One

Number of participants included planned: 100

General information of the research study

Study design: single-center, experimental, prospective, longitudinal, parallel with 2 groups (1:1), randomized, *double-blinded*

Statistical considerations: Eligible patients will be randomized via computer-generated random permuted blocks (block sizes of 10), stratified by the number of set-up markings (≤ 4 vs. >4), to one of two possible groups. To guarantee the concealment of the attribution, a computer-generated list will be prepared by a person external to the study, which will serve for the preparation of closed white envelopes, of the same size, sequentially numbered, opaque and sealed, which will be distributed by the principal investigator to the TC simulation technicians.

Objectives: To compare two set-up tattooing systems: lancet-based vs. *Comfort Marker 2.0®* system.

Inclusion criteria:

1. Patients referred to the External Radiotherapy Service for external beam RT;
2. Patients in need of set-up markings as an inherent part of the Radiotherapy process;
3. Age ≥ 18 years at the date of the first radiation oncology consultation;
4. Good *performance status* (ECOG PS 0-1)
5. RT treatments with an estimated fractionating schedule of ≥ 13 once-daily fractions;
6. The signing of informed consent.

Exclusion criteria:

1. Patients requiring either immobilization thermoplastic masks (for head or head and shoulders) or vacuum cushion
2. Patients referred to the external radiotherapy service under an inter-hospital protocol.

Criteria to be evaluated :

1. Patients' comfort (Pain inherent to the tattoo procedure);
2. Radiation therapists' satisfaction (Evaluation of the ease of application of the markings);
3. **Effectiveness** (set-up markings visibility across RT fractions);
4. Fading across RT fractions;
5. Fading at 6 months after tattoo application;
6. inadvertent sharps injuries.

[figure not shown]
Considerations for *Comfort Marker 2.0* ®

The *Comfort Marker 2.0* ® device consists of a Control Unit and a Pen Module, the latter being responsible for activating the marking needle.

For the present study, the *Comfort Marker 2.0* ® system will be transferred to the Portuguese Institute of Oncology in Porto, free of charge, without any charges. This will consist of 1 *Medical Precision Comfort Marker 2.0* (consisting of the control unit and its Pen) and 1 *Medical Precision Patient Marking Set* (which includes: 50 needles, 50 pigments, and 50 pigment containers).

Study planning:

Attachments

Questionnaire 1

Research study: Tattooing of skin set-up markings in Radiotherapy: comparison between the traditional system and the Comfort Marker 2.0®

[figure not shown]
Patient ID

1. Randomization Arm: Lancets Comfort Marker 2.0

2. Set-up Markings:

2.1. Number of markings tattooed:

2.2. Localization (identify in the figure with sequential numbering):

Nr	Depth (mm)	Nr	Depth (mm)
1		9	
2		10	
3		11	
4		12	
5		13	
6		14	
7		15	
8		16	

3. Inadvertent sharps injuries.: Yes No

If yes, explain the event.

4. Assessment of the ease of tattooing: Easy Medium Hard

5. Patient-reported pain assessment:

0 – none 10 - worst imaginable pain

If more than one reference mark is made, assign an overall score.

0	1	2	3	4	5	6	7	8	9	10
---	---	---	---	---	---	---	---	---	---	----

Date: ____/____/_____

Signature: _____

[figure not shown]
Mec. number: _____

Annex 3: Questionnaire 1

Questionnaire 2

Research study: Tattooing of skin set-up markings in Radiotherapy: comparison between the traditional system and the Comfort Marker 2.0®

Patient ID

1. Quality assessment of the patient set-up markings:

Note: Perform the assessment for EACH set-up marking.

Nr of tattoo	Data	Quality				Evaluator (Mec. nr)
		Bad	Reasonable	Good	Very Good	
1						
2						
3						
4						
5						
6						
7						
8						

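### Is one kit of 50 Comfort Marker sets too few for the arm that stratified blocks of 10 can produce?

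*Protocol*

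**What the plan says.** Under *Identification of the research study* the protocol gives "Number of participants included planned: 100". Under *General information of the research study* the design is "parallel with 2 groups (1:1), randomized", and the allocation method is "computer-generated random permuted blocks (block sizes of 10" and "stratified by the number of set-up markings (≤ 4 vs. >4". The list is prepared by someone outside the study and delivered in sealed, numbered envelopes.

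Under *Considerations for Comfort Marker 2.0* the protocol says that the "system will be transferred to the Portuguese Institute of Oncology in Porto, free of charge, without any charges". The transfer consists of one device and one marking set, "which includes: 50 needles, 50 pigments, and 50 pigment containers".

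The protocol does not say how many needles, pigments or containers one patient uses. It mentions no spare or practice sets, and it neither provides for nor rules out further supply.

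**The concern.** Fifty sets for an arm of nominally 50 leaves no margin, and the arm size is not fixed at 50. A complete block of 10 puts five patients in each arm, but recruitment stops at 100 patients in total, not at the end of a block in each stratum. Each stratum can therefore finish part-way through a block, and both unfinished blocks can lean towards Comfort Marker.

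If the last set were used and the next envelope said Comfort Marker, the site would have to give lancets, withdraw the patient, defer the patient or find another set. The first three depend on the allocation just revealed, and so depart from the concealed randomisation that the envelopes protect. The protocol has no rule for this case. A failed needle, or sets used for familiarisation by staff who currently work with lancets, would make a shortage more likely.

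**Working it through.** **Inputs from the protocol.** Total 100; ratio 1:1; block size 10 (five per arm in a complete block); two strata; 50 sets in the kit.

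**Assumptions, not stated in the protocol.** One set per patient; no wastage; no supply beyond the kit. The share of patients in each stratum is not given, so it is varied.

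**1. Nominal arm.** 100 × 1/2 = 50, which equals the kit.

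**2. Actual arm.** Let r be the remainder when the size of one stratum is divided by 10.
- If r = 0, both strata end on complete blocks and the arm is 10 × 5 = 50.
- Otherwise there are (100 − 10)/10 = 9 complete blocks, contributing 9 × 5 = 45. The two unfinished blocks hold r and 10 − r patients, so

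arm = 45 + Hypergeometric(10, 5, r) + Hypergeometric(10, 5, 10 − r).

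**3. Worked case, r = 5.** Each unfinished block gives 0 to 5 Comfort Marker patients with weights 1, 25, 100, 100, 25, 1 out of 252. For two blocks the denominator is 252² = 63,504.
- P(51) = 15,050 / 63,504 = 0.237
- P(52) = 5,200 / 63,504 = 0.082
- P(53 or more) = 876 / 63,504 = 0.014
- P(55) = 1 / 63,504 = 0.000016
- P(more than 50) = 21,126 / 63,504 = 0.333

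**4. All remainders.**

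| r | P(>50) | P(≥52) | P(≥53) | Maximum |
|---|---|---|---|---|
| 0 | 0 | 0 | 0 | 50 |
| 1 or 9 | 0.250 | 0 | 0 | 51 |
| 2 or 8 | 0.296 | 0.049 | 0 | 52 |
| 3 or 7 | 0.319 | 0.076 | 0.007 | 53 |
| 4 or 6 | 0.329 | 0.091 | 0.012 | 54 |
| 5 | 0.333 | 0.096 | 0.014 | 55 |

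**5. Averages, with r equally likely from 0 to 9.**
- P(>50) = (0 + 2 × 0.250 + 2 × 0.2963 + 2 × 0.3194 + 2 × 0.3294 + 0.3327) / 10 = 0.272
- P(≥52) = (2 × 0.0494 + 2 × 0.0764 + 2 × 0.0913 + 0.0957) / 10 = 0.053
- P(≥53) = (2 × 0.0069 + 2 × 0.0119 + 0.0138) / 10 = 0.005

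The overrun is exactly one patient in 0.272 − 0.053 = 0.219 of trials and exactly two in 0.053 − 0.005 = 0.048. Among trials with an overrun, 1 − 0.005/0.272 = 98% are over by one or two.

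**6. Sensitivity to the stratum share.** With binomial stratum sizes, P(>50) is 0.257 to 0.272 for shares of 10% to 90%, and 0.309 at 5%. The probability of 55 is about 1 to 3 per million. A 40,000-run simulation with equal strata gave 27.3%.

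**7. Wastage.** The distribution is symmetric about 50. With 49 usable sets the kit falls short when the arm is 50 or more: 1 − 0.272 = 73% of trials. With 48 it falls short when the arm is 49 or more: 1 − 0.053 = 95%.

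**8. Effect on the result if a shortage were handled badly.** Suppose the one surplus patient received lancets and was analysed as randomised. One of 51 is 2.0% of the arm. If that patient's outcome were typical of lancets, the difference between arms would shrink to 50/51 = 0.98 of its size. For two of 52 it would be 50/52 = 0.96.

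**The case for a change.** The strongest argument for acting is the lack of reserve. One dropped or practice set turns a shortage from a one-in-four event into a likely one (73%), and two lost sets make it close to certain (95%). A shortage would fall at the end of recruitment, when the allocation can no longer be arranged around it, and staff who count sets could see it coming. The remedy is cheap: 55 sets cover every possible allocation of 100 patients, before wastage.

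The arithmetic stands, and so does the practical advice to keep spares. The step from there to a fault in the plan does not.

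- That the kit is the total supply is a reading the text does not make. The section describes what is donated. Obtaining a few more sets is open to the site, and it removes the choice between lancets, withdrawal and deferral.
- One set per patient is also assumed. Heavier use would exhaust the kit well before the end, and the site would have to reorder for that reason alone.
- The idea that early Comfort Marker patients would be learning cases, biasing ease, quality and pain against the device, has no support in the text. The protocol says lancets are the current method and is silent on training. The heading *Study planning* has no text under it in the copy read, and figures are missing, so silence proves little.
- Closing recruitment at ten complete blocks would fix the arm at 50, but it would refuse eligible patients in one stratum and would still not cover wasted sets.

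**Conclusion.** No change to the plan is needed. One kit is not guaranteed to cover the Comfort Marker arm, but it does so in about 73% of trials if each patient uses one set and none is wasted. In the remaining 27% or so the shortfall is almost always one or two sets. The ceiling of 55 needs both strata to end with five patients left over and all ten of them allocated to Comfort Marker; it has no practical weight.

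No figure in the protocol is wrong, no two sections contradict each other, and neither the randomisation scheme nor any comparison depends on the kit size. Even a mishandled shortage of one or two patients would dilute the difference between arms by about 2% to 4%. The remaining matter is one of stock: know the use per patient and hold a few spares, with more if sets are used for practice. A site handles that without amending its protocol, and writing it in would bring no material gain in the validity of the results.

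### The pain item does not ask for tattoo-caused pain only and has no pre-tattoo score, so other pain can enter the first-listed criterion

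*Protocol*

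**What the plan says.** Under Criteria to be evaluated, item 1 is patients' comfort, defined as "Pain inherent to the tattoo procedure". The protocol lists it first but does not label it primary.

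The only visible measure is Questionnaire 1, item 5. Its heading is "Patient-reported pain assessment", its anchors are "0 – none 10 - worst imaginable pain", and its one instruction is "If more than one reference mark is made, assign an overall score". The item just above it names its object: "Assessment of the ease of tattooing: Easy Medium Hard".

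Inclusion criterion 1 is "Patients referred to the External Radiotherapy Service for external beam RT". Other criteria require ECOG 0-1 and at least 13 once-daily fractions, and exclude patients needing masks or vacuum cushions and inter-hospital referrals. None concerns existing pain or analgesic use. The design is "parallel with 2 groups (1:1), randomized", with 100 patients planned and stratification by number of markings only.

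**The concern.** The criterion is about pain from one brief procedure, but the question is worded as a general pain rating. Patients referred for radiotherapy may already have pain. The Background section also places the marking after CT simulation in the planning position with immobilisation supports, so discomfort from the position is a second possible source. The item does not tell the patient to leave these out, and no earlier score exists from which an analyst could separate them.

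Three things are at stake for this criterion:

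- precision of the arm comparison;
- the size of the observed device difference, if other pain masks procedural pain;
- the meaning of each arm's mean as a level of procedural pain.

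An SAP cannot repair this later. It can neither adjust for a score that was not collected nor clarify a question already answered.

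**Working it through.** The protocol gives no figure to reproduce here: the readable text states no SD, effect size or power for pain. The check has two parts.

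**1. Reading the form.** Criterion 1 names the tattoo procedure as the source of the pain. Item 5 does so only indirectly: its instruction says how to combine several marks into one score, which points the patient to the marks but does not exclude other pain. The readable form has a date field but no time of rating relative to the marks, and no pre-tattoo item.

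**2. Size, on assumed values.** From the protocol: 100 patients at 1:1, so n = 50 per arm. Everything else below is an assumption.

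*Gain from a pre-tattoo covariate.* With correlation r between pre-tattoo and recorded pain, residual variance is multiplied by 1 − r² and the standard error by √(1 − r²).

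| r | 1 − r² | SE factor | SE reduction |
|---|---|---|---|
| 0.3 | 0.91 | 0.954 | about 5% |
| 0.5 | 0.75 | 0.866 | about 13% |
| 0.6 | 0.64 | 0.800 | 20% |

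*Cost of unadjusted background pain.* Take a true difference of 1 point, tattoo-pain SD 2.0, independent background pain with SD b that adds to the score, and two-sided alpha 0.05. Total SD is σ = √(2.0² + b²). Power is Φ(1/(σ√(2/50)) − 1.96). The difference detectable at 80% power is (1.96 + 0.84) × σ × √(2/50).

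| b | σ | Power | Detectable difference |
|---|---|---|---|
| 0 | 2.00 | 70.5% | 1.12 |
| 1.0 | 2.24 | 60.9% | 1.25 |
| 1.5 | 2.50 | 51.6% | 1.40 |
| 2.0 | 2.83 | 42.4% | 1.58 |

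The two tables agree: b = 1.5 implies r = 1.5/2.5 = 0.6, and 2.5 × 0.800 returns the SD of 2.0. Over b = 0 to 2.0, power falls from 91.5% to 51.6% if the tattoo-pain SD is 1.5, and from 51.6% to 34.5% if it is 2.5.

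*Bias and dilution.* A simulation used 1,000,000 patients per arm. Tattoo pain had means 3 and 2 and SD 2, rounded and bounded to 0-10. Background pain of 1-5 points was present in 10%, 30% or 50% of patients.

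- Equal devices: the arm difference stayed within 0.002 of zero in every setting.
- Unequal devices (0.89 after bounding), background pain adding to the score: the difference was 0.888, 0.884 and 0.872.
- Unequal devices, patients reporting the worse of their two pains: it was 0.853, 0.752 and 0.655.

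In the last case the SD in the higher-pain arm also fell (1.889, 1.833, 1.752). The standardised difference therefore falls from 0.853/1.889 = 0.45 to 0.655/1.752 = 0.37, proportionately less than the raw difference.

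**The case against.** The strongest reply is that item 5, read whole, already asks about the marking. Its instruction refers to the reference marks, the form carries the tattooing study's title, the neighbouring items are about tattooing, and the criterion itself is explicit. This stands against a stronger reading that a reader might infer, namely that the score has no link to the tattoo and that existing pain is counted in it. The documents do not say so; they only fail to rule out that other pain enters.

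Randomisation is the second reply, and it also stands. Background pain and time in position cannot systematically favour an arm, and chance imbalance is already reflected in the standard error. A baseline score is not needed for an unbiased comparison.

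Third, ECOG 0-1 and the minimum of 13 fractions may limit background pain, and the documents give no prevalence. The largest dilution above needs both half the patients in pain and worst-pain reporting.

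Fourth, the two parts of the fix overlap: if rewording removes the other pain, r falls and the covariate gains little. At r = 0.1, √(1 − 0.01) = 0.995, a gain of only 0.5%.

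Finally, figures are missing from the readable text and the forms appear to be translated (Annex 4 is marked as being in Portuguese), so fuller instructions may exist. None of these replies supplies an explicit attribution to the tattooing, a rating time or an earlier score.

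**Conclusion.** The point holds as a wording and data-collection weakness of minor to moderate importance. As shown, item 5 leaves room for pain other than that caused by the tattooing, and nothing on the form allows it to be separated afterwards. The consequences are extra variance, possible dilution if patients report their worst current pain, and arm-level scores that may overstate procedural pain.

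It would go too far to call the comparison biased between arms or the score uninterpretable: allocation is randomised 1:1, and the item does refer to the marks. The 5% to 20% reduction in standard error rests wholly on the assumed correlation of 0.3 to 0.6. The power and dilution figures rest on assumed SDs, a 1-point difference and assumed background-pain patterns. They show direction and plausible scale, and are not estimates for this trial.

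**What to change.** Revise Questionnaire 1 in three steps:

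1. Reword item 5 to ask for pain caused by the tattooing, rated immediately after the last mark, and keep the 0-10 scale and the single overall score.
2. Add the same 0-10 question, about current pain, in the planning position just before the first mark and before the patient can know the arm.
3. State that the arm comparison on item 5 uses the pre-tattoo score as a covariate.

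The rewording comes first, because covariate adjustment may not fully undo worst-pain reporting. The pre-tattoo score covers what the rewording does not remove. If the original-language form already carries this attribution and timing, step 1 reduces to showing it in the protocol.

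The cost is a form revision and one question of about ten seconds. Asking beforehand may slightly anchor the later answer, which should be similar in both arms.

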Annex 4: Questionnaire 2 (in Portuguese)
